IOP/OP Patient Identification. Study staff will connect with and cultivate relationships with outpatient treatment programs to inform case workers and clinical staff about the study and treatment options being offered to encourage referrals for patients who are presenting for treatment. We will accept referrals for patients not currently engaged in primary care, or for those willing to change primary care providers. Patients referred from OP settings will be screened by an RA using the CO-Triage. Those that pre-qualify will be referred to a participating FQHC upon their discharge for further assessment (see below).

Advertising. We will also recruit through advertisements (e.g., radio, newspaper, billboards, yellow pages listings, informational brochures). All advertisements will include a study hotline that will be directed to a study RA. Callers will be screened using the CO-Triage, and those that are not currently engaged in primary care, or are willing to change primary care providers will be referred to a participating FQHC upon their discharge for further assessment (see below). All advertisements will be approved by the IRB.

Screening

Research assistants (RAs), BHCs, and other FQHC staff will screen patients offsite and in the host FQHCs using the CO-Triage as described above. Patients who meet screening criteria for Level 1 or 2 care on the CO-Triage will be invited to complete the ASAM Criteria Software interview to determine if they meet study criteria.

Patients who are identified as potential study participants through the processes described above will be asked to complete a screening consent with an RA. We are requesting a waiver of written documentation of consent for the screening process. According to 45 CFR 46.117(c), written documentation may be waived if “the only record linking the subject and the research would be the consent document and the principal risk would be potential harm resulting from breach of confidentiality.” The screening consent form would be the only written document linking the patient to the research, thus a requirement for written consent would paradoxically be the only real danger to loss of privacy and confidentiality for participants who agree to be screened. We will provide an information sheet to patients prior to screening that contains informed consent information, and we will obtain verbal consent that the patient is willing to participate in the screening.

For patients who consent to screening, an RA or BHC will administer the ASAM Criteria Software interview to determine if they meet DSM-V criteria for a Moderate to Severe OUD diagnosis with ≥ 4 symptoms and opioid use within the past month. Patients meeting criteria must also affirm that they are not currently engaged in primary care (no provider, or no PC contact in the past year), and be willing to receive care at the participating FQHC. Eligible patients will then be invited to complete informed consent with an RA.

Inclusion and Exclusion Criteria

Inclusion Criteria: 1) patient is 18 years or older, 2a) they meet the criteria for Level 1 care, i.e., outpatient treatment, as defined by the ASAM Criteria, and determined for the patient’s needs according to the decision engine built into the ASAM Criteria Software, or 2b) they meet criteria for Level 2 care (Level 2.0), i.e., intensive outpatient program..

Exclusion Criteria: (a) the medical practitioner or BHC overrule these criteria because medical and psychiatric complications exist that would contraindicate research participation; (b) they have an ASAM level of care higher than 2.0, (c) the patient reports plans to leave the area (i.e. Philadelphia or Washington DC greater metropolitan area) within the next 6 months; (d) the patient is not English-speaking; (e) if the patient is unable to provide valid informed consent by correctly describing the key components of consent to the RA.

Informed Consent

During the informed consent process, patients will be fully informed of the procedures, the nature of the study conditions, the randomization procedure, inclusion and exclusion criteria for the study, and the compensation associated with participating in the study. They will be informed which research data may be part of their medical record (as specified above in item 7), and which research data collected in the study will be kept strictly confidential. The only exceptions to confidentiality (clearly specified in the consent forms) will pertain to information related to medical emergencies, disclosure of current child/elder/dependent abuse or neglect, or imminent risk of death or serious injury to the participant or others. Potential participants will also be informed of all known potential risks and benefits of participation, their right to refuse or revoke consent at any time, and the names and phone numbers of individuals they may contact for additional information or to register complaints about study procedures. They will also be asked to complete a brief consent quiz to ensure their understanding of the study requirements, the risks and benefits, and their human subject protections. All items answered incorrectly will be reviewed until the potential participant demonstrates at least a 95% understanding of the essential elements of the informed consent document. Potential participants will then be asked if they have any questions and will be asked to sign the informed consent form to document their agreement to participate. They will receive a duplicate copy of the consent form for their records. The original signed consent form will be kept in a locked filing cabinet only accessible to research staff.

10. Discuss whether risks to the subject are ‘minimal’ or ‘greater than minimal.’ List the major risks of subject participation. Describe any possible benefits of subject participation. Are the risks to subjects reasonable in relation to the anticipated benefits to subjects and in relation to the importance of the knowledge that may reasonably be expected to result?

There are six anticipated potential risks associated for participants enrolled in this study. The procedures for minimizing these risks are detailed below in item 11.

1. Perception of coercion: It is possible that some participants may feel coerced to participate in the research study. Our previous studies with similar populations indicate that this is a rare event.
2. Discomfort answering research questions and/or providing biological data: Participants may experience mild and transitory psychological discomfort from completing research measures that deal with emotionally laden material or from providing urine or hair samples. The probability of these risks and the magnitude of the anticipated harm are likely to be small. These events have *not* been encountered in any of our previous studies using similar assessments.
3. Discomfort associated with the treatment intervention: Participants may experience emotional distress given that the interventions are designed to encourage them to become more aware of their own substance use behaviors and how those behaviors may be impacting their physical and psychological wellbeing. We expect this level of distress to be similar to that which patients would experience during any psychological or psychoeducational intervention, and thus is not a function of research participation per se. We have not encountered any instances of significant emotional upset with individuals who have participated in our previous investigations of psychosocial interventions.
4. Possible side effects from medication assisted treatment (MAT): As part of this study, participants in the PATH condition will be offered access to MAT as part of their suite of treatment options. No participant will be forced to engage in MAT; the decision about whether MAT is appropriate will be made by the participant and their medical provider. However, if a patient is in the PATH condition, the patient and provider decide that MAT is appropriate, and the patient is inducted onto medication, then the patient may be at risk for possible side effects from the MAT. Importantly, our intervention is making only FDA approved medications available for appropriate indications.
5. Harm from breach of confidentiality: Participants are at risk for harm as a result of being identified as a study participant or as someone with an opioid use problem. The likelihood of this occurring is small.
6. Discomfort associated with allowing semi-structured interviews to be audio recorded (for process evaluation only): Patients who participate in the interviews for the process evaluation may experience mild and transitory psychological discomfort when their interviews are being audio-recorded. The probability of these risks and the magnitude of the anticipated harm are likely to be small.

Benefits to Participants: Participants may benefit from receiving an intervention (either SC or PATH) which is designed to help patients achieve abstinence or reduction in opioid use and retention in treatment.

Importance of Knowledge to be Gained: The aim of this project is to test the impact of a PATH approach to assist opioid-dependent patients in reducing substance use and improving related outcomes. If PATH proves to be effective, patients will demonstrate detectable reductions in substance use and higher engagement rates with OUD treatment during the 18-month follow up period. We will also measure other outcomes of great importance to stakeholders, patients, and their families such as medical functioning, employment, and quality of life outcomes.

11. Describe the procedures for protecting against or minimizing any potential risks, including physical, psychological, legal and confidentiality risks, and assess their likely effectiveness. Where appropriate, discuss provisions for insuring necessary medical or professional intervention in the event of adverse events to the subjects and for monitoring the data collected to insure the safety of subjects. Also, where appropriate, describe alternative treatment and procedures that might be advantageous to the subjects.

1. Perception of coercion: The RAs will be trained to describe the study to eligible patients, including the risks and benefits, prior to offering an invitation to participate in the study. The RA will clearly state that the patient's decision to participate is voluntary and that it will not impact the services they would otherwise receive at the health center. In addition, patients will be told that health center staff have no vested interest in their participation and will receive no benefit if they choose to participate. All potential participants will be told that if they feel any pressure to participate from anyone they can voice this concern to the FQHC staff, the PI, or other TRI research staff, and the PI will discuss this matter with the health center director and/or other appropriate individuals.
2. Discomfort answering research questions and/or providing biological data: Individuals in any study may experience mild and transitory emotional discomfort when answering the questions posed in interviews and on questionnaires, or providing a urine or hair sample. All participants will be informed about these possible risks before signing the consent form. Urine samples collected for research purposes only will not be collected under observation. Samples collected from PATH patients for contingency management will be collected under observation by health center medical assistants. Urine collection staff and research staff will complete a training regarding monitoring and addressing emotional distress among research participants, and a training on the urine and hair collection process which will include suggestions for decreasing participant discomfort. Participants will be told that they can choose not to respond to a question that they find upsetting and can withdraw from participation at any time without negative consequence.
3. Discomfort associated with the treatment interventions: Participants may experience mild and transitory psychological discomfort while participating in the treatment interventions. [name] (Co-I) and the Clinical Supervisor will jointly train the BHCs to monitor patient participants for distress by observing their behavior during their assessment and intervention sessions. This training will focus specifically on helping patients to manage difficult feelings, screening them for potential harm to self and others, and implementing methods to help ensure their physical safety and emotional well-being. If necessary, the BHCs can obtain timely clinical consultation about the participant's distress by contacting the Clinical Supervisor.
4. Possible side effects from MAT: If the patient and his/her provider decide that MAT is appropriate, and the patient is inducted onto medication, then the patient may be at risk for side effects from the MAT. To minimize this risk, the providers trained to deliver MAT in this study will be fully trained on how to appropriately and safely prescribe MAT. Providers will also be trained to thoroughly advise patients about the possible known side effects associated with each medication. Our team will also monitor for frequency of expected and unexpected side effects, intervene when appropriate, and will report side effects of unusual manifestation or unusual frequency to the IRB and DSMB.
5. Harm from breach of confidentiality: Identifiable data collected for study purposes only will be kept strictly confidential and will not be shared with anyone outside of the research team. Data collected as a part of the patients' medical records will also be kept confidential per site HIPAA regulations. The only exceptions to confidentiality (clearly specified in the consent form) will be for information related to medical emergencies, child abuse or neglect, or imminent risk of death or serious injury to the participant or others. All research specific materials will be coded with a research number to de-identify the data and will contain no other identifying information. Information collected on paper (e.g., consents) will be stored in locked filing cabinets at TRI or the participating health centers. Computer spreadsheets will be saved in password-protected files. Participants will be assigned an

identification number which will be affixed to all collected data. Linkage between participant identity and identification numbers will be stored in a password protected electronic file available only to designated research staff. All research instruments will be computerized for this study, and the data will be entered via the Web into the secure ASAM Criteria system and a secure server located at the University of Pennsylvania's Data Management Unit. Efforts to contact participants for follow-ups will make no mention of the study until it is established that the participant has been reached. Access to participants' contact information will be limited only to research staff members who need to contact a participant for study purposes. Should any breaches of confidentiality occur, they will be reported to the relevant IRB, DSMB, and PCORI officials.

6. Discomfort associated with recorded interviews (for process evaluation only): This risk applies only to patients who agree to participate in the semi-structured interviews for the process evaluation. This level of distress is likely to be similar to other situations when people are audio-recorded or videotaped for any purpose. Usually, if any discomfort is experienced, it is very temporary. Participants will be reminded during the informed consent process that their responses are confidential and will be de-identified, and that their interviews will not be shared with anyone other than appropriate research personnel, and will be erased within five years after the completion of the study. During informed consent, participants can choose to have their interview responses typed up by research staff if they do not wish to be audio-recorded; participants who agree to be recorded can ask to stop the recording at any time. Digital audio recordings of process evaluation interviews will be coded/saved with the date of the session and an interview code; no personal identifying information will be placed in the filename or intentionally dictated into the audiotape. Research staff who are responsible for transcribing the content will also be responsible for erasing identifying information from the audiotape and ensuring that identifying information does not appear in the transcript. All digital audio files will be destroyed no later than 5 years after completion of the study.

12. Describe procedures for reporting Serious Adverse Events (SAEs) and Adverse Events (AEs), and Unanticipated Problems. Include the definition of SAEs and AEs.

Serious Adverse Events (SAEs) will be defined as 1) death or 2) a life threatening event such as suicide attempt or inpatient hospitalization due to psychiatric distress, drug/alcohol overdose, or severe reaction to a prescribed medication. A component of the study interventions involves referral to specialty treatment, including inpatient hospital-based treatment as appropriate. Admission to hospital-based inpatient substance use treatment will not be defined as an SAE unless, as noted above, it occurs as a result of or in conjunction with clinical worsening, overdose, or complications due to alcohol/drug use. Childbirth, pre-planned elective procedures, and unrelated medical events that require hospitalization will not be considered SAEs. Participants in this study are substance dependent and are thus at risk for clinical worsening. Although we do not believe the study procedures or intervention places participants at increased risk for clinical worsening, we will review and report events of clinical worsening that leads to hospitalization. These events are not anticipated to occur on a regular basis.

Adverse Events (AEs) will be defined as report of coercion to participate in the study; significant discomfort from answering research questions or providing urine/hair samples such that the participant decides to stop their participation; significant discomfort or distress from participating in the intervention; significant discomfort or distress from having process interviews audio-taped; negative side effects due to breach of confidentiality; significant increase in drug/alcohol use or psychiatric symptoms compared to baseline; suicidal ideation; or adverse reactions to MAT. For patients on MAT, we will consider any reaction to the medication that is not a known side effect to be an AE. We will also consider any severe reaction to a medication to be an AE, even if the reaction is a known side effect. We will monitor attrition rates, but drop out from the study will not be reported as an AE. Clinically insignificant

events (e.g., cold/flu, common headache) are not considered AEs. Participants may have medical and psychiatric problems which may continue during the course of the study. As per the definition of AEs, only significant worsening of baseline medical and psychiatric status or new problems will be reported as AEs. The AEs listed above have been known to occur in prior research with substance dependent populations. However, due to the protections put in place we do not anticipate reports of coercion to participate; significant discomfort from answering research questions, providing urine/hair samples, participating in the intervention, or recorded interviews; or side effects due to breach of confidentiality. Substance abuse and psychiatric disorders are often chronic relapsing diseases, and therefore we anticipate a small percentage of clients will report an increase in drug/alcohol use or psychiatric symptoms during their participation in the study. However, as stated above we will only report these if they are a significant increase from baseline.

All adverse and serious adverse events occurring during the study are documented on a form, reviewed and signed by the Co-PIs or Co-I and reported to TRI and other applicable IRBs. All SAEs are reported to the IRBs within 48 hours of our awareness of the event (24 hours for fatal events). A summary of all SAEs and AEs that occurred during the previous year will be included on the annual progress report to the relevant IRBs.

13. If this study is a chart review, indicate the time frame of data to be collected (from when to when). Also, will the data be collected anonymously (meaning that only aggregate data will be collected, and there will be no names or codes maintained to match the data with the original files)?

We will collect data from participants' charts at the health centers and substance use treatment centers as part of this study. This information will include the client's name, discharge status, individual and group counseling attendance, prescribed medications and dosage, and results of urine drug tests at the treatment center. We will collect this information beginning on the participant's study enrollment date and ending on the date the client completed involvement in the study. The data will not be collected anonymously, as we will need to link the chart data to specific participants in order to determine study outcomes. However, we will de-identify all research data collected from the charts; this data will be linked and stored under the participants' research identification numbers. All chart data will be provided to TRI by the participating health and treatment centers.

14. Children, defined as individuals under the age of 21, must be considered for potential enrollment in every study as subjects unless there are scientific or ethical reasons for excluding them. See below for the permissible exclusionary circumstances listed in the NIH Policy. If no exclusion applies: 1) discuss your plan for the inclusion of children; 2) justify the age range of children to be enrolled; 3) indicate the expertise of the research team with regard to children; 4) describe the facilities for the children; 5) indicate the number of children to be enrolled to give sufficient power for meaningful analysis; 6) describe how the assent process for children 7 to 18 years of age will be carried out.

Justify your exclusion based on one of the exclusionary circumstances listed:

- The research topic is irrelevant for children
- Children are barred by law from participation because of the risk
- Study is redundant; knowledge is being obtained in another study or is already available
- Separate age-specific children study is preferable
- Rarity of disorder makes inclusion of children extremely difficult

- The limited number of available children are already enrolled in a nation-wide pediatric disease network
- Study design precludes direct applicability to children
- Insufficient adult data to judge potential risk for children
- Study design is a follow-up of an adult study

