Medication Support. Patients receiving either medication will be given initial and ongoing support to increase understanding of the role of medicine (e.g., foundational and stabilizing, but requiring psychosocial treatment), the medication options, and differences in side effects and risks. Periodic re-evaluation will examine with the patient his/her progress towards goals and, in the event of less than anticipated progress, review the contingency plan (e.g., medication or dose changes, co-occurring disorder management, and escalation of recovery support).

2. Cognitive-Behavioral / Relapse Prevention with Contingency Management: The BHC will deliver manualized cognitive-behavioral relapse prevention (CB/RP) along with contingency management (CM). During Weeks 1-13, patients in the PATH condition will come to the FQHC twice per week for CM and CB/RP sessions. CB/RP will then continue with once weekly sessions in Weeks 14-26, and as needed but tapering in frequency for Weeks 27-52. Procedures for CM and CB/RP are as follows:

Urine Sample Collection and Testing. Patients will be scheduled to provide urine samples twice weekly prior to seeing the LCSW for their regular counseling visits, which will be separated by 2 or 3 days. Samples will be collected under direct observation by a same-sex staff member. Valid samples will be tested for Opioids using quick read test strips at the cutoff levels established by SAMHSA to indicate substance abstinence (specific testing materials to be determined by the FQHC's billing and reimbursement practices). Urinalysis results will be entered into a database that calculates the value of the voucher to be delivered.

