3. Recovery Support Services: Peer Recovery Specialists will work with the BHC to aid the patient in social service needs, help patients stay motivated and connected and begin focusing on personal recovery goals. Patients will set goals with the Peer Specialist and professional SUD treatment team to improve housing and employment, family / social functioning, manage child care, develop supportive relationships and establish a daily routine. The Peer Recovery Specialist will help the patient access community resources, and offer longitudinal peer / relational support. The Peer Recovery Specialist also provides a model of a recovery lifestyle. If a patient goes missing, the Peer Specialist will seek out the patient by telephone or through contacts and re-engage them.

Follow-up Procedures

We will complete follow-up assessment interviews with participants at 3-, 6-, 9-, 12-, 15- and 18-months post-baseline. Follow-up assessments will take place in-person, generally at the FQHC site. If the participant is not able to travel to the FQHC (or they have been discharged and are not allowed back on the premises), then we will meet them in a safe, neutral location such as a restaurant or public library. The assessment battery will be similar to that collected at Baseline (see Item #7), and we will collect a hair and urine sample. If a participant is incarcerated at any follow-up point research staff will not attempt to contact the participant while incarcerated.

We will also call participants every month that a follow-up assessment is not due (i.e. months 1, 2, 4, 5, 7, 8, 10, 11, 13, 14, 16, and 17) to verify the Locator information they provided at baseline, and update any information that has changed.

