The measures listed below are collected for research purposes only and will not become part of patients' medical records. These measures will be stored separately from those collected as part of the medical record, and only TRI researchers will be able to link this data to the patient.

Weekly during Weeks 1 through 6, Pilot Study Only:

Weekly Timeline Followback (TLFB): The TLFB [42] is a structured interview which helps patients recall their substance use to reflect a specified period. Patients are presented with a calendar representing the past 7 days, and the interviewer helps the patient anchor the calendar with memorable events to reconstruct their use (dates, amounts) over the designated period.

Baseline and Follow-up Instruments (administered at Baseline, 3-, 6-, 9-, 12-, 15-, and 18 month follow-ups):

Urine testing: On-site urine drug testing kits (ACON International) rapidly (5-minute) test for cocaine, opiates, amphetamines, methamphetamines, benzodiazepines, cannabis, barbiturates, PCP, and alcohol. Urine testing will be administered at all follow-ups to capture very recent use (i.e. past 3 days).

Hair follicle testing: Hair follicle samples will be sent to an accredited laboratory for testing. Samples generally provide a 90-day window of use, and will be tested for opiates, cocaine, amphetamines, methamphetamines, ecstasy, marijuana, and PCP. If a hair sample of 1.5 inches cannot be provided, urine sampling only will be performed.

Non-Study Medical and Other Services (NSMOS): This questionnaire was adapted from the Treatment Services Review [43,44] for patients in medical settings. The NSMOS counts substance abuse treatment, medical services, visits to medical offices, hospitalizations, and emergency room visits received that were not a part of the assigned treatment.

FQHC / SUD Treatment Program Case Review: Chart review will verify patient self-report of treatment engagement. We will obtain the first version of this data by pulling payment data from funders. We will resolve inconsistencies between patient report and billing data through chart review.

Texas Christian University Treatment Engagement (TCU ENGForm): The TCU ENGForm [45] measures patient therapeutic engagement in and satisfaction with substance abuse treatment. It includes 36 items from four scales representing Treatment Participation, Treatment Satisfaction, Counseling Rapport, and Peer Support, and it takes approximately 10 minutes to complete.

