Primary Hypothesis 1: Clients in the PATH condition will demonstrate higher rates of confirmed substance abstinence (hair and UA verified) during treatment and at follow-up than clients in the SC condition. Confirmed abstinence is the “gold standard” of direct clinical outcomes in SUD research. A mixed effects logistic regression model [2,3] will be used to compare the binary outcome of hair and urinalysis-confirmed abstinence in the two treatment conditions at months 3, 6, 9, 12, 15, and 18. Mixed effects models have advantages of traditional repeated measures approaches in that they allow for missing observations, accommodate measurements made at different time points, provide flexibility in modeling the variance-covariance matrix, and permit the estimation of both group and random patient-specific effects. The model will include terms for treatment condition, time, and their interaction, and the binary baseline abstinence variable along with any other necessary covariates. We will follow the recommendations of Varadhan and Seeger [4] to test heterogeneity of treatment effect (HTE). We have identified two primary subgroup analyses to be performed: (1) setting [IP (n = 400) vs. OP (n = 400)] and (2) type of opioid [heroin (n = 534) vs. prescription (n = 266)]. We will use similar mixed effects logistic regression models (described above) that will additionally include terms for the specific subgroup variable and its interaction with treatment condition. In the event that the interaction is significant, the treatment effect will be estimated separately at each level of the categorical variable that is used to define the subgroups. In addition, we will conduct an *exploratory* subgroup analysis for medication type (agonist vs. antagonist/drug free). We anticipate simple time trends (e.g., linear or quadratic) for the mixed effects models; however, we will use linear spline models in the event complex time trends are observed, such as non-linear trends that cannot be approximated by simple polynomials in time [2]. These analyses will be performed using PROC GLIMMIX.

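### Research urine for the abstinence outcome is unobserved with no stated validity check, so at visits without a hair result a substituted or diluted sample could pass

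*Protocol*

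**What the plan says.** - **Outcome.** The SAP (Primary Hypothesis 1) compares the arms on a binary outcome, abstinence confirmed by hair and urinalysis, at months 3, 6, 9, 12, 15 and 18. It comments: "Confirmed abstinence is the “gold standard” of direct clinical outcomes in SUD research".
- **Research urine.** Protocol item 11, under risk 2: "Urine samples collected for research purposes only will not be collected under observation". Staff are trained in collecting urine and hair, but the only content described is how to reduce discomfort. The urine-testing entry in item 7 gives the kit, the substances tested and a window of about 3 days. It gives no check on the specimen itself.
- **Place.** Follow-ups are generally at the FQHC. If a participant cannot attend, "then we will meet them in a safe, neutral location such as a restaurant or public library" (Protocol item 6, Follow-up Procedures).
- **Hair.** Hair is due at every follow-up, covers about 90 days and includes opiates. The fallback in item 7 is: "If a hair sample of 1.5 inches cannot be provided, urine sampling only will be performed". Neither document says how often this is expected or how such a visit is scored.
- **Voucher urine, PATH only.** These samples do not define the outcome, yet the procedure is stricter: "Samples will be collected under direct observation by a same-sex staff member. Valid samples will be tested for Opioids using quick read test strips" (Protocol item 6, Urine Sample Collection and Testing). The criteria for a valid sample are not given there either.
- **Other data on use.** Chart urinalysis results and self-reported use are collected. The SAP uses self-report only as an alternative outcome definition in a sensitivity analysis, and no rule brings either source into the primary outcome.

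**The concern.** An unobserved sample with no integrity check can be substituted or diluted. When hair is present this matters little for opiates, because recent use should show in the hair. When hair is absent, a negative strip is the only biological evidence for that visit. If the visit is then scored as abstinent, the word confirmed rests on a specimen that nobody has shown to be the participant's undiluted urine.

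False negatives at the same rate in both arms raise both abstinence rates and shrink the difference between them, which costs power. This is separate from the short urine window. That problem concerns genuine urine that misses older use; this one concerns whether the specimen is genuine. Validity cannot be checked once the sample is discarded, so it has to be settled before enrolment.

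**Working it through.** **Inputs from the documents** (Protocol item 5; SAP, Power for the Primary Hypotheses): SC abstinence 25%, within-patient correlation 0.50, alpha 0.025, 20% attrition at the final time point, 400 per arm overall, 133 per arm in the smallest subgroup. Six follow-ups come from the SAP, Primary Hypothesis 1. Sidedness is not stated; two-sided reproduces the plan's figures (critical value 2.241). I apply the 20% loss throughout.

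**Step 1: reproduce the plan's power.** The variance factor for a six-visit average is (1 + 5 × 0.5)/6 = 0.583.

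Smallest subgroup, 25% vs 40%:
- effective n per arm = 133 × 0.8 / 0.583 = 182.4
- SE = √[(0.25 × 0.75 + 0.40 × 0.60)/182.4] = 0.0484
- power = Φ(0.15/0.0484 − 2.241) = 80% (79.6% with a pooled null variance). The plan states 80%.

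Full sample:
- effective n per arm = 320/0.583 = 548.6
- for 25% vs 33.4%, SE = √[(0.25 × 0.75 + 0.334 × 0.666)/548.6] = 0.0273
- power = Φ(0.084/0.0273 − 2.241) = 79.7%. The plan states about 8 points, OR 1.5, at 80%.

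The plan's power figures are not in error on this point.

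**Step 2: model the gap.** Three quantities are assumptions, since the documents give none of them:
- h = share of visits that are urine-only
- x = share of truly urine-positive samples at those visits that read negative through substitution or dilution
- u = share of non-abstinent patients who would be urine-positive

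Hair is taken to catch use at all other visits, and a urine-only negative is taken to be scored as abstinent. The observed rate in each arm is then q = p + (1 − p) × u × h × x, and the observed difference is 0.084 × (1 − u × h × x). Use older than the urine window is left out.

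**Step 3: results, same rates in both arms.**

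| u | h | Power at x = 10% | x = 20% | x = 30% |
|---|---|---|---|---|
| 0.5 | 10% | 79% | 78% | 77% |
| 0.5 | 30% | 77% | 75% | 73% |
| 1.0 | 10% | 78% | 77% | 75% |
| 1.0 | 30% | 75% | 71% | 66% |

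Worked case, u = 0.5, h = x = 30%: u × h × x = 0.045. SC is 0.25 + 0.75 × 0.045 = 28.4%, PATH is 0.334 + 0.666 × 0.045 = 36.4%, and the difference is 8.0 points instead of 8.4. With SE 0.0282, power is 73%.

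Extreme case, u = 1: u × h × x = 0.09, the rates are 31.8% and 39.4%, the difference is 7.6 points and power is 66%.

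At h = 0, q = p and nothing is lost.

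**The case against.** Much of the case on the other side stands.

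- **Hair guards the outcome.** A reader might infer that any falsified urine is scored as verified abstinence. The documents do not support that: the outcome also needs hair, which is due at every follow-up and covers opiates. The gap is confined to urine-only visits.
- **The scoring is not written down.** Neither document says a urine-only negative counts as abstinent. The visit could equally be treated as missing or non-abstinent. The concern is conditional on that choice, and the missing rule is itself part of the point.
- **Other evidence exists.** It would be too strong to say that nothing else could catch a false sample, since chart urinalysis and self-report could flag discordance. No rule feeds them into the primary outcome, however, and the observed voucher samples exist by protocol only in PATH and only in weeks 1–13.
- **Vouchers do not bias the comparison.** A reader might infer that PATH patients have more reason to falsify. But vouchers are calculated from separate, observed samples. Research results stay out of the medical record, and the $50 payment is for completing the assessment. Vouchers also overlap at most the month-3 visit. Even if 20% of PATH and 10% of SC non-abstinent patients passed at that visit, with 30% urine-only and a true rate of 25%, the gap there would be 0.75 × 0.30 × 0.10 = 2.25 points. Averaged over six visits that is 2.25/6 = 0.4 points, and false rejection is about 2.6% against 2.5%.
- **Level of detail.** Cup features may sit in an operating manual, and silence in the protocol does not prove absence. That is fair, but a rule on invalid samples decides how the primary outcome is scored, so it belongs in the protocol and SAP.

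**Conclusion.** The point holds in a limited form. Research urine is unobserved, may be collected off site, has no stated validity check, and stands alone when hair is too short. The likely consequence is modest attenuation: power falls from about 80% to between 79% and 73% if half of non-abstinent patients would be urine-positive, with 66% as the low end if all would be.

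These figures rest on assumed rates for urine-only visits and for samples that pass, on equal rates in both arms, and on urine-only negatives being scored as abstinent. The loss is nil if hair is always obtained, provided abstinence is judged on substances in the hair panel; benzodiazepines, barbiturates and alcohol are on the urine panel only. The documents do not establish a bias in favour of either arm. The plan gives no expected frequency of missing hair, so it cannot show that the problem is negligible, and the remedy is cheap.

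**What to change.** 1. **Protocol items 7 (Urine testing) and 11 (risk 2).** Keep collection unobserved. Require research urine to be collected in cups with a temperature strip and dilution/adulterant pads, read at collection.
2. **Invalid samples.** Re-collect an out-of-range sample at the same visit. If it is still invalid and hair is missing, do not score the visit as confirmed abstinent.
3. **SAP, Primary Hypothesis 1.** State how a valid urine-only negative is scored.
4. **SAP, Sensitivity analyses.** Repeat the Primary Hypothesis 1 analysis on visits with a hair result only. A restriction that also kept valid urine-only visits would not isolate the problem.

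Cost: slightly dearer cups, one form field and a few repeat samples. No extra visit or staff is needed.
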